**Table JPBQ.9.1. Treatment Regimens/Dosing Schedule**

Regimen	Period/Cycle	Dose Day
Arm A1		
Abemaciclib	Treatment/28-day cycle	150 mg PO Q12H on Days 1-28
Anastrozole or Letrozole	Treatment/28-day cycle	1 mg PO Q24H on Days 1-28 a or 2.5 mg PO Q24H on Days 1-28 a
Arm A2b		
Placebo	Treatment/28-day cycle	PO Q12H on Days 1-28
Anastrozole or Letrozole	Treatment/28-day cycle	1 mg PO Q24H on Days 1-28 a or 2.5 mg PO Q24H on Days 1-28 a
Arm B1		
Abemaciclib	Treatment/28-day cycle	150 mg PO Q12H on Days 1-28
Fulvestrant	Treatment/28-day cycle	500 mg IM on Days 1 and 15 of Cycle 1, then Day 1 of Cycle 2 and beyond c
Arm B2d		
Placebo	Treatment/28-day cycle	PO Q12H on Days 1-28
Fulvestrant	Treatment/28-day cycle	500 mg IM on Days 1 and 15 of Cycle 1, then Day 1 of Cycle 2 and beyond c

Abbreviations: IM = intramuscular; NSAI = nonsteroidal aromatase inhibitor; Q12H = once every 12 hours; Q24H = once every 24 hours; PK = pharmacokinetic; PO = orally.

a For PK purposes, NSAI should be administered at the same time (or up to 20 minutes after) the first dose of blinded study drug through Cycle 4, Day 1. Subsequently, the interval between administration of blinded study drug and NSAI may be adjusted based on the judgment of the investigator.

b For patients in Arm A2 who crossover to Arm A1, the Arm A1 treatment schedule should be followed.

c For PK purposes, fulvestrant should be administered at the same time as (or up to 20 minutes after) the first dose of blinded study drug, except when specified otherwise in the PK Sampling Schedule ([Attachment 7](#)) through Cycle 4 Day 1. Subsequently, the interval between administration of blinded study drug and fulvestrant may be adjusted based on the judgment of the investigator.

d For patients in Arm B2 who crossover to Arm B1, the Arm B1 treatment schedule should be followed.

The investigator or his/her designee is responsible for the following:

- explaining the correct use of the drugs and planned duration of each individual's treatment to the patient/site personnel/legal representative,
- verifying that instructions are followed properly,
- maintaining accurate records of study drugs dispensing and collection, and
- returning all unused medication to Lilly or its designee at the end of the study.

**Note:** In some cases, sites may destroy the material if, during the investigator site selection, the evaluator has verified and documented that the site has appropriate facilities and written procedures to dispose clinical trial materials.

Patients will be instructed to contact the investigator as soon as possible if they have a complaint or problem with the study drug or drug delivery system so that the situation can be assessed.

## 9.2. Materials and Supplies

Abemaciclib or placebo (blinded study drug) will be supplied as capsules for oral administration. Blinded study drug capsules should be stored according to the product label, and not opened, crushed, or dissolved. Blinded study drug will be labeled according to the country's regulatory requirements.

Where required, letrozole, anastrozole, and fulvestrant will be supplied by Lilly and labeled according to country regulatory requirements. All drugs should be stored according to the product label and will be provided as anastrozole 1-mg and letrozole 2.5-mg tablets or fulvestrant 250-mg prefilled syringes (250 mg/5 mL).

Investigators should instruct patients to store the blinded study drug and NSAI in the original package provided and in a location inaccessible to children.

Fulvestrant should be stored according to the instructions on the product label and administered according to the instructions in the protocol.

## 9.3. Method of Assignment to Treatment

Upon obtaining informed consent, site personnel should access the interactive web response system (IWRS). Patients who meet all criteria for enrollment will be randomly assigned to receive either abemaciclib plus NSAI/fulvestrant or placebo plus NSAI/fulvestrant. Assignment to treatment groups will be determined by a computer-generated random sequence using the IWRS. Sites will be prompted to enter the specific NSAI at time of randomization for patients in Cohort A.

Randomization will be stratified by the following in Cohort A: nature of disease (visceral metastases vs. non-visceral metastases), and prior (neo)adjuvant endocrine therapy (prior therapy with disease-free interval > 12 months from completion of treatment vs. prior therapy with disease-free interval ≤ 12 months from completion of treatment vs. no prior therapy).

Randomization will be stratified by the following in Cohort B: nature of disease (visceral metastases vs. non-visceral metastases) and sensitivity to endocrine therapy (primary resistance vs. secondary resistance).

The IWRS will be used to assign abemaciclib or placebo and distribute NSAI/fulvestrant supplied by Lilly (except distribution of NSAI in China). Site personnel will confirm that they have located the correct study medication packages by entering a confirmation number found on the packages into the IWRS.

The period between randomization to blinded study drug and the first dose (Cycle 1, Day 1) should not exceed 7 days.

## 9.4. Selection and Timing of Doses

Blinded study drug will be taken orally every 12 ( $\pm 2$ ) hours on Days 1 through 28 of a 28-day cycle, for a total of 56 doses per cycle. During all cycles, blinded study drug should be taken at approximately the same times each day. If a patient misses or vomits a dose, that dose should be omitted.

Anastrozole or letrozole will be administered orally every 24 hours ( $\pm 2$ ) on Days 1 through 28 of a 28-day cycle for a total of 28 doses per cycle. For PK purposes, anastrozole or letrozole should be administered at the same time as (or up to 20 minutes after) the first dose of blinded study drug through Cycle 4, Day 1. Subsequently, the interval between administration of blinded study drug and anastrozole or letrozole may be adjusted based on the judgment of the investigator. If a patient misses or vomits an anastrozole or letrozole dose, that dose should be omitted.

Fulvestrant will be administered intramuscularly on Days 1 and 15 of Cycle 1, then on Day 1 of Cycle 2 and beyond. For PK purposes, fulvestrant should be administered at the same time as (or up to 20 minutes after) the first dose of blinded study drug, except when specified otherwise in the PK Sampling Schedule ([Attachment 7](#)) through Cycle 4, Day 1. Subsequently, the interval between administration of blinded study drug and fulvestrant may be adjusted based on the judgment of the investigator.

In the event of a dose suspension of blinded study drug due to toxicity at the beginning of a cycle, the PK Sampling Schedule may require adjustment. In these exceptional circumstances, the sponsor should be notified.

A cycle is defined as an interval of 28 days plus any subsequent delay prior to start of the next cycle. A delay in the start of a cycle due to holidays, weekends, bad weather, or other unforeseen circumstances will be permitted up to 7 days and not counted as a protocol deviation).

A patient may continue to receive study treatment until she meets 1 or more of the specified reasons for discontinuation (as described in [Section 7.3](#)).

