### 10.1. Efficacy Measures

#### 10.1.1. Efficacy Assessments at Baseline and during Study Treatment

Within 28 days of randomization, baseline tumor measurements will be performed on each patient. The method of assessment used at baseline must be used consistently for serial tumor assessment throughout the study. Computed tomography (CT), including spiral CT, scans and magnetic resonance imaging (MRI) are the preferred methods of measurement. In addition, bone scintigraphy will be performed for all patients at baseline (within 28 days of randomization). However, prior bone scintigraphy (obtained as part of routine clinical care) within 45 days before Day 1 of Cycle 1 is also acceptable.

For all patients, imaging studies (CT, including spiral CT, or MRI scan of the chest, abdomen, and pelvis) will be performed locally at baseline and repeated between last 7 days of every second cycle beginning with Cycle 2 and continuing through Cycle 18, in the last 7 days of every third cycle after Cycle 18 (inclusive), and within 14 days of clinical progression per the Study Schedule ([Attachment 1](#)). It is recommended that CT imaging of the abdomen and pelvis be performed with IV contrast, whenever possible. For patients with known hypersensitivity to CT contrast material, a CT scan of the chest without contrast and gadolinium-enhanced MRI of the abdomen and pelvis are encouraged. The CT portion of a positron emission tomography (PET)-CT scan may be used as a method of response assessment if the site can document that the CT is of identical diagnostic quality to a diagnostic CT (with IV and oral contrast). A PET scan alone or as part of a PET-CT may be performed as part of routine clinical care but cannot be used to assess response according to RECIST v1.1.

For only those patients with bone lesions identified by bone scintigraphy at baseline, directed imaging using 1 of the following methods will be performed at baseline: X-ray, CT scan with bone windows, or MRI. Directed imaging using the same method as at the baseline bone lesion assessment should be repeated between last 7 days of every second cycle beginning with Cycle 2 and continuing through Cycle 18, in the last 7 days of every third cycle after Cycle 18 (inclusive), and within 14 days of clinical progression.

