### **10.1.2. Efficacy Assessments during the Study Period Postdiscontinuation Follow-Up**

Postdiscontinuation follow-up during the study period will be conducted as described in the Study Schedule ([Attachment 1](#)).

For those patients who are randomized and never receive study treatment or those who discontinue study treatment without objectively measured PD, the investigative sites will continue to monitor patients and periodically evaluate tumor response approximately every 8 weeks for the first 18 months following randomization and thereafter approximately every 12 weeks by the same method used at baseline and throughout the study until the patient has objective disease progression, or until the primary analysis of PFS. In addition, anticancer therapies initiated after study treatment discontinuation will be collected during this follow-up period. After the patient has objective disease progression, radiologic imaging and photographic images are no longer required and the patient will be followed up approximately every 12 weeks ( $\pm 14$  days) until the patient's death or overall study completion.

After study completion, efficacy assessments (frequency and type of assessments) will be at the discretion of the investigator.

Lilly will continue to collect survival data on all patients but may reduce data collection for other efficacy data. Lilly will notify investigators when this reduced data collection can begin.

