## 12. Sample Size and Statistical Methods

### 12.1. Determination of Sample Size

The primary objective of this study is to compare abemaciclib plus NSAI versus placebo plus NSAI in terms of PFS in postmenopausal women with HR+, HER2- locoregionally recurrent or metastatic breast cancer.

The key secondary objective of this study is to compare abemaciclib plus fulvestrant versus placebo plus fulvestrant with respect to PFS for postmenopausal women with HR+, HER2- locoregionally recurrent or metastatic breast cancer.

The study plan is to enroll approximately 450 patients in total, with 300 HR+, HER2- locoregionally recurrent or metastatic breast cancer patients who have not received prior endocrine therapy in Cohort A and 150 HR+, HER2- locoregionally recurrent or metastatic breast cancer patients in Cohort B. Assuming approximately 10% screening failure, the study will enter approximately 500 patients.

The approximate 300 patients qualified for Cohort A will be randomized in a 2:1 ratio to Arm A1 (abemaciclib plus NSAI; 200 patients) and Arm A2 (placebo plus NSAI; 100 patients). Patients will be randomized using the following stratification factors: nature of disease (visceral metastases vs. non-visceral metastases) and prior (neo)adjuvant endocrine therapy (prior therapy with disease-free interval > 12 months from completion of treatment vs. prior therapy with disease-free interval ≤ 12 months from completion of treatment vs. no prior therapy).

A 2-look group-sequential design of the primary endpoint will be used to accommodate an event-driven plan for the interim and primary PFS analyses (see Section 12.2.6 for details). The primary PFS analysis will be performed after approximately 170 PFS events in Cohort A have occurred (ie, approximately 43% censoring rate). Assuming a hazard ratio of 0.626, this sample size yields about 81.40% statistical power to detect superiority of the abemaciclib plus NSAI arm over the placebo plus NSAI arm with the use of a 1-sided log-rank test and a type I error of 0.025. If the true median PFS for the placebo plus NSAI arm is 14.4 months, then the hazard ratio of 0.626 amounts to an approximately 8.6-month (59.7%) improvement in median PFS for the abemaciclib plus NSAI arm under an additional assumption of exponential survival distribution.

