Abbreviations: BL = baseline; BP = blood pressure; CT = computed tomography; CTCAE = Common Terminology Criteria for Adverse Events; ECG = electrocardiogram; ECOG = Eastern Cooperative Oncology Group; EORTC QLQ-C30 = European Organization for Research and Treatment of Cancer Quality of Life Questionnaire-Core 30; FSH = follicular stimulating hormone; HR = heart; IV = intravenous; mBPI-sf = modified Brief Pain Inventory short form; MRI = magnetic resonance imaging; NSAI = nonsteroidal aromatase inhibitor; PD = progressive disease; PK = pharmacokinetics; Q12H = every 12 hours; Q24H = every 24 hours; RECIST = Response Evaluation Criteria in Solid Tumors; RR = respiratory rate; SAE = serious adverse event; temp = temperature.

- a Short-term follow-up begins the day after the patient and the investigator agree that the patient will no longer continue study drug and lasts approximately 30 days ( $\pm 7$  days); the associated study procedures are performed once at the end of this period. Long-term follow-up begins the day after short-term follow-up is completed and continues until the patient's death or overall study completion; the associated study procedures are performed approximately every 12 weeks ( $\pm 14$  days) for the duration of this period.
- b For Cycle 2 and beyond, the start of a cycle may be delayed up to 7 days for logistical reasons and up to 14 days to allow sufficient time for recovery from toxicity possibly related to a study drug. Refer to Section 9.4.1.1.2.
- c Informed consent form is signed within 28 days prior to randomization of study drug and prior to performance of any protocol-specific tests/procedures.

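### On-treatment scans follow cycles that toxicity can lengthen; if abemaciclib cycles are delayed more often, PFS is biased in its favour and one-sided type I error could reach about 3.1-4.4% under assumed delay rates

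*Protocol*

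**What the plan says.** - **Cycle length.** Protocol 9.4: "A cycle is defined as an interval of 28 days plus any subsequent delay prior to start of the next cycle".
- **On-treatment imaging.** Protocol 10.1.1 places scans "between last 7 days of every second cycle beginning with Cycle 2 and continuing through Cycle 18", then at the end of every third cycle. Attachment 1, footnote e, repeats this.
- **Cycle delay.** Attachment 1, footnote b, lets the start of Cycle 2 and later cycles slip up to 7 days for logistics and "up to 14 days to allow sufficient time for recovery from toxicity possibly related to a study drug". Section 9.4.1.1.2 allows longer by agreement with the sponsor physician.
- **Off-treatment imaging.** Patients who stop treatment without objective progression are scanned "approximately every 8 weeks for the first 18 months following randomization" and about every 12 weeks after that (Protocol 10.1.2).
- **Dating of events.** Protocol Table JPBQ.12.1 and SAP Table JPBQ.6.1, rule 5, date progression at the assessment that documents it.
- **Error control.** Protocol 12.1 plans the Cohort A comparison "with the use of a 1-sided log-rank test and a type I error of 0.025".
- **Sensitivity analyses.** SAP 6.7.3, Analysis 3, moves progressions found at unscheduled scans to the next scheduled one. No listed analysis looks at unequal timing of scheduled scans.

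**The concern.** The scan clock runs on cycles, and a cycle can be stretched by toxicity. The protocol names diarrhea and neutropenia among the common events possibly related to abemaciclib, and Table JPBQ.9.2 makes suspension mandatory for several grades of both. A higher rate of cycle delay on abemaciclib is therefore plausible, although no rate is given.

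If it occurs, placebo scans tend to come a few days earlier in each scan round. Placebo progressions are then dated first, while abemaciclib patients with the same underlying progression time are still counted as at risk. The log-rank test reads that ordering as benefit. At stake is whether the primary test keeps its stated one-sided level of 0.025. The protocol already uses a schedule without this weakness for patients off treatment, but not for patients on it.

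**Working it through.** **1. Reproduce the plan's figure.** Inputs from Protocol 12.1 and 12.2.6: 170 events, hazard ratio (HR) 0.626, 2:1 allocation ("Arm A1 (abemaciclib plus NSAI; 200 patients) and Arm A2 (placebo plus NSAI; 100 patients"), one-sided 0.025, interim at 119 events.
- Single look: z = √(170 × 2/3 × 1/3) × |ln 0.626| − 1.96 = 6.146 × 0.468 − 1.96 = 0.919, so power is 82.1%.
- Two looks with the printed boundaries (one-sided 0.0082 and 0.0223): power 81.41%, alpha 0.0250. This matches the stated 81.40%.
- HR needed at the final look: exp(−2.008/6.146) = 0.72.

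**2. What a shifted null HR does to alpha.** For one look, alpha = 1 − Φ(1.96 − 6.146 × |ln HR|).
- HR 0.975: 1 − Φ(1.96 − 0.156) = 3.56% (two looks: 3.54%).
- HR 0.96: 1 − Φ(1.96 − 0.251) = 4.37% (two looks: 4.33%).
- An alpha of 4.0% with two looks needs HR of about 0.966.

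**3. Simulate the schedule under the null.** There were 60,000 trials per case with 200 v 100 patients. Both arms had exponential PFS with median 14.4 months (the control median in Protocol 12.1). Scans fell on days 22-28 of Cycles 2, 4, ... 18 and then of every third cycle. Delays accumulated by arm, and both looks used the printed boundaries. HR is exp(mean of score/information).

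Assumptions not in the documents: uniform accrual over 14 months; the delay rates; delays uniform on 1-14 days unless noted; every patient stays on the cycle schedule; no stratification.

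| Cycles delayed, abemaciclib v placebo | Null HR | One-sided alpha |
|---|---|---|
| none | 0.996 | 2.8% |
| 10% v 10% | 0.995 | 2.8% |
| 5% v 5%, at most 7 days | 0.996 | 2.7% |
| 3% v 2% | 0.989 | 3.1% |
| 5% v 2% | 0.980 | 3.5% |
| 10% v 2% | 0.967 | 4.1% |
| 10% v 2%, at most 7 days | 0.961 | 4.4% |
| 10% v 5% | 0.980 | 3.4% |
| 15% v 5% | 0.972 | 3.8% |
| 20% v 5% | 0.972 | 3.9% |
| 20% v 10% | 0.978 | 3.6% |
| 30% v 5% | 0.981 | 3.5% |
| 50% v 5% | 0.996 | 3.1% |

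The Monte Carlo standard error of alpha is about 0.07-0.08 points. Measured from the 2.8% reference, unequal delay adds 3.1 − 2.8 = 0.3 to 4.4 − 2.8 = 1.6 points. The 0.3-point excess of the reference over 2.5% appears with no delay at all, so it cannot be charged to the schedule. The effect rises and then falls with the delay rate because the test responds to the order of scans within a round.

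**The case against.** **The NSAI rule.** Section 9.4.1.1.2 says that if the endocrine partner is given while blinded drug is suspended, its administration date is Day 1 of the next cycle. In Cohort A the NSAI is taken daily, Table JPBQ.9.2 governs blinded drug only, and a hold within a cycle need not extend it. Cycles may therefore seldom lengthen. This is the strongest argument, and it limits the problem, but it does not settle it. Sections 9.4.1.1.3 and 9.4.1.1.4.1 suspend study treatment, which Protocol 9.1 defines with an and/or and SAP 6.1.2 defines as drug plus partner. A drug taken daily also does not identify one particular Day 1.

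**Dilution.** Logistical delays occur in both arms, and clinical progression triggers a scan within 14 days. In a separate run of 15,000 null trials per case (standard error about 0.15 points), the 10% v 2% case gave 4.3%. Logistical delay in 20% of cycles in both arms reduced this to 3.5%. Clinically triggered scans in 20% of patients as well reduced it to 3.25%. With those logistical delays, 3% v 1% gave 3.1% and 2% v 1% gave 2.8%; no delay gave 2.7%. These rates are assumed too, but the point stands: small differences diluted in this way are nearly harmless.

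**Footnote b.** A reader might take it to permit holding both drugs for up to 14 days. It says only that a cycle start may be delayed, and it refers to the section that contains the NSAI rule.

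**Timing.** The protocol is at amendment (e). Re-anchoring scans in a running trial would mix two schedules within patients. That is a fair reason to prefer the SAP route if follow-up is well advanced.

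**Conclusion.** The mechanism and its direction follow from the protocol's text, and no planned analysis would reveal it. Its size depends on delay rates that the documents do not give. With about 3-50% of abemaciclib cycles delayed against 2-5% of placebo cycles, the null HR is about 0.96-0.996 and one-sided type I error about 3.1-4.4%, against 2.7-2.8% with no or equal delays. The effect shrinks towards that reference if the NSAI rule keeps cycles at 28 days.

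A shift of this size is small beside the design HR of 0.626. It would matter for a result near the final threshold of about 0.72, not for a large effect.

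A reader might infer that the design itself moves the null HR to 0.975 and type I error to 4%. The documents do not support that: it needs assumed delay rates, it passes over the NSAI rule, and the two figures do not pair, since a uniform shift to 0.975 gives 3.5-3.6%. Nor does more delay always mean more bias: 50% v 5% gives 3.1%. This is a cheap improvement to the plan, not an error in it.

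**What to change.** - **Schedule.** In Protocol 10.1.1 and Attachment 1, set on-treatment imaging by weeks from randomization regardless of cycle delays, with the existing 7-day window. Cost: protocol wording, and some scans no longer coincide with cycle visits. It needs no more scans than the undelayed schedule already plans. It removes the part due to unequal delay, not the 0.3-point excess seen without any delay.
- **If the trial is too far advanced.** Add to SAP 6.7.3 a PFS sensitivity analysis that assigns each progression to its nominal scheduled assessment date, or that uses interval-censored methods. Report actual scan intervals by arm. This costs programming only.
- **Reconcile.** Protocol 9.1, 9.4, 9.4.1.1.2, 9.4.1.1.3, 9.4.1.1.4.1 and Attachment 1 footnote b should agree on what is suspended and when the next cycle starts. The off-treatment calendar should also agree: Section 10.1.2 and footnote e use 8-weekly scans for 18 months, while footnotes d and g use 12 months.

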### 9.4.1. Special Treatment Considerations

#### 9.4.1.1. Dose Adjustments and Delays

Toxicity dose adjustments and delays of blinded study drug for this study are summarized in [Table JPBQ.9.2](#).

**Table JPBQ.9.2. Toxicity Dose Adjustments and Delays of Blinded Study Drug for Study JPBQ**

Toxicity Type	Toxicity Profile and Severity	Dose Suspension	Dose Reduction
Hematologic Toxicity Section 9.4.1.1.3	Grade 3	Dose MUST be suspended until toxicity resolves to at least Grade 2.	Dose MAY be reduced by 1 dose level at investigator's discretion.
Hematologic Toxicity Section 9.4.1.1.3	Recurrent Grade 3 within 8 weeks	Dose MUST be suspended until toxicity resolves to at least Grade 2.	Dose MUST be reduced by 1 dose level.
Hematologic Toxicity Section 9.4.1.1.3	Grade 4	Dose MUST be suspended until toxicity resolves to at least Grade 2.	Dose MUST be reduced by 1 dose level.
Hematologic toxicity: If patient requires administration of blood cell growth factors Sections 9.4.1.1.3 and 9.6.4	Regardless of severity (Use growth factors according to ASCO Guidelines)	Dose MUST be suspended for at least 48 hours after the last dose of blood cell growth factors was administered and until toxicity resolves to at least Grade 2.	Dose MUST be reduced by 1 dose level unless already performed for incidence of toxicity that led to the use of growth factor.
Nonhematologic Toxicity b (except diarrhea and ALT increased) Section 9.4.1.1.4	Persistent or recurrent Grade 2 that does not resolve with maximal supportive measures within 7 days to baseline or Grade 1	Dose MUST be suspended until toxicity resolves to either baseline or Grade 1.	Dose MUST be reduced by 1 dose level.
Nonhematologic Toxicity Section 9.4.1.1.4	Grade 3 or 4	Dose MUST be suspended until toxicity resolves to either baseline or Grade 1.	Dose MUST be reduced by 1 dose level.
Diarrhea Sections 9.4.1.1.4.1 and 9.6.5	Grade 2 that does not resolve within 24 hours to at least Grade 1	Dose MUST be suspended until toxicity resolves to at least Grade 1.	Dose reduction is NOT required.
Diarrhea Sections 9.4.1.1.4.1 and 9.6.5	Persistent or recurrent Grade 2 that does not resolve with maximal supportive measures, or any Grade of diarrhea that requires hospitalization	Dose MUST be suspended until toxicity resolves to at least Grade 1.	Dose MUST be reduced by 1 dose level.
Diarrhea Sections 9.4.1.1.4.1 and 9.6.5	Grade 3 or 4	Dose MUST be suspended until toxicity resolves to at least Grade 1.	Dose MUST be reduced by 1 dose level.
ALT Increased (Sections 9.4.1.1.4.2. and 10.3.3.1)	Persistent or recurrent a Grade 2 (>3.0-5.0×ULN), or Grade 3 (>5.0-20.0×ULN) c	Dose MUST be suspended until toxicity resolves to baseline or Grade 1.	Dose MUST be reduced by 1 dose level.

ALT Increased (Sections 9.4.1.1.4.2 and 10.3.3.1)	Grade 4 (>20.0×ULN)	Blinded study drug MUST be discontinued.	Blinded study drug MUST be discontinued.
ALT Increased with increased total bilirubin, in the absence of cholestasis (Sections 9.4.1.1.4.2)	Grade 3 increased ALT (>5.0 × ULN) with total bilirubin >2 × ULN	Blinded study drug MUST be discontinued	Blinded study drug MUST be discontinued

Abbreviation: ALT = alanine transaminase; ASCO = American Society of Clinical Oncology.

Note: MUST = mandatory.

- a Determination of persistent events will be at the discretion of the investigator. Recurrent toxicity refers to the same event occurring within the next 8 weeks (as measured from the stop date of the preceding event). As a general guidance, based on the risk/benefit balance assessment per the investigator, for a patient who experiences a new episode of Grade 3 hematological toxicity after more than 8 weeks following the last episode of same Grade 3 hematological toxicity, the investigator may consider resuming the patient on the same drug dose should the patient satisfy the following conditions:
- shows stable hematological counts (Grade ≤2) during that timeframe
  - has absence of any signs or risk of infection
  - is benefiting from study treatment
- b Additional guidance for renal and hepatic monitoring is in Sections 10.3.3.1 and 10.3.3.2
- c Grade 3 ALT increased is a trigger for additional assessments and possibly hepatic monitoring. See Section 10.3.1.1 for additional guidance for hepatic monitoring

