#### **9.4.1.1.4.1. Diarrhea**

A patient experiencing diarrhea requiring hospitalization (irrespective of grade, that is, requiring intravenous [IV] rehydration) or severe diarrhea (Grade 3 or 4; see [Attachment 9](#)) must have study treatment suspended (until the toxicity resolves to at least Grade 1) and must have the blinded study drug dose reduced by 1 dose level as outlined in [Table JPBQ.9.3](#).

If a patient experiences persistent or recurrent diarrhea that does not resolve with maximal supportive measures (refer to Section [9.6.5](#)) within 24 hours to at least Grade 1, then study treatment must be suspended (until the toxicity resolves to at least Grade 1) and the dose of blinded study drug must be reduced by 1 dose level as outlined in [Table JPBQ.9.3](#).

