#### **9.6.5. Supportive Management for Diarrhea**

At randomization, patients should receive instructions on the management of diarrhea. In the event of diarrhea, supportive measures should be initiated as early as possible. These include the following:

- At the first sign of loose stools, the patient should initiate anti-diarrheal therapy (eg loperamide) and notify the investigator/site for further instructions and appropriate follow-up.
- Patients should also be encouraged to drink fluids (eg, 8 to 10 glasses of clear liquids per day).
- Site personnel should assess response within 24 hours
- If diarrhea does not resolve with anti-diarrheal therapy within 24 hours to at least Grade 1, blinded study drug should be suspended until diarrhea is resolved to at least Grade 1.
- When blinded study drug recommences dosing should be adjusted as outlined in Section 9.4.1.1.1.1 and Table JPBQ.9.3.

In severe cases of diarrhea, the measuring of neutrophil counts and body temperature and proactive management of diarrhea with antidiarrheal agents should be considered.

If diarrhea is severe (requiring IV rehydration) and/or associated with fever or severe neutropenia, broad-spectrum antibiotics such as fluoroquinolones must be prescribed.

Patients with severe diarrhea or any grade of diarrhea associated with severe nausea or vomiting should be carefully monitored and given intravenous fluid (IV hydration) and electrolyte replacement.

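### Section 9.6.5 points towards a dose reduction after any diarrhoea unresolved at 24 hours, whereas Table JPBQ.9.2 requires only suspension for a first Grade 2 episode, and Section 9.4.1.1.4.1 leaves the boundary unclear

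*Protocol*

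**What the plan says.** Four places in the protocol bear on the restart dose after Grade 2 diarrhoea.

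- **Table JPBQ.9.2, first diarrhoea row.** The trigger is "Grade 2 that does not resolve within 24 hours to at least Grade 1". Suspension is mandatory; on the dose the row says "Dose reduction is NOT required".
- **Table JPBQ.9.2, second diarrhoea row.** The trigger is "Persistent or recurrent Grade 2 that does not resolve with maximal supportive measures, or any Grade of diarrhea that requires hospitalization". Suspension and a one-level reduction are both mandatory, and the row gives no time limit.
- **Section 9.4.1.1.4.1.** After a paragraph on hospitalized and Grade 3 or 4 diarrhoea, the rule begins "If a patient experiences persistent or recurrent diarrhea that does not resolve with maximal supportive measures", continues "within 24 hours to at least Grade 1, then study treatment must be suspended", and ends with the requirement that "the dose of blinded study drug must be reduced by 1 dose level as outlined in" Table JPBQ.9.3. It names no grade and has no counterpart to the table's first row.
- **Section 9.6.5.** The condition is "If diarrhea does not resolve with anti-diarrheal therapy within 24 hours to at least Grade 1". Study drug is then to be suspended until Grade 1. The next bullet says dosing on restart is to be adjusted according to Section 9.4.1.1.1.1 and Table JPBQ.9.3. Table JPBQ.9.2 is not mentioned.

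Three further provisions matter. Footnote a to Table JPBQ.9.2 leaves persistence to the investigator and defines recurrence as the same event within 8 weeks. Section 9.4.1.1.2 allows restart at the same or a reduced dose after a within-cycle suspension, and requires reduction if the same toxicity, at the same or greater severity, forces another suspension. Section 9.4.1.1.1.1 says reductions must follow Table JPBQ.9.3 and permits re-escalation only after consulting the sponsor's physician.

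**The concern.** A site treating a first Grade 2 episode that has lasted 24 hours finds a suspend-only rule in the table. The table's diarrhoea rows refer the site to Sections 9.4.1.1.4.1 and 9.6.5, and neither contains that rule. Section 9.6.5 sends the site to a section about reducing the dose. Section 9.4.1.1.4.1 uses the same 24 hours, but for a mandatory reduction. Section 9.4.1.1 describes the table as a summary, and none of these sections says which text prevails.

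Diarrhoea heads the list of common, possibly drug-related events in both the Synopsis and the Introduction, so sites should expect to use these rules. A reduction is also hard to undo. Table JPBQ.9.3 has two steps below 150 mg (100 mg and 50 mg Q12H), re-escalation needs sponsor consultation, and under Section 7.3.2 an adverse event that would call for a third reduction is a reason to stop study drug. A reduction that the table does not require can therefore use up one of two steps. Conversely, a site that restarts at 150 mg under the table could be recorded as departing from 9.6.5.

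**Working it through.** No design figure is involved, so the check applies each rule to the same three patients. All have Grade 2 diarrhoea that has not come down to Grade 1 after 24 hours of treatment, and none is hospitalized. In the second and third cases the diarrhoea continues despite maximal supportive measures.

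| Source | First episode, not judged persistent | First episode, judged persistent | Recurrence within 8 weeks |
|---|---|---|---|
| Table JPBQ.9.2 | Row 1: suspend, reduction not required | Row 2: suspend, reduce one level | Row 2: suspend, reduce one level |
| Section 9.4.1.1.4.1 | Not addressed | Suspend, reduce one level | Suspend, reduce one level |
| Section 9.6.5 | Suspend, restart at adjusted dose | Suspend, restart at adjusted dose | Suspend, restart at adjusted dose |
| Section 9.4.1.1.2 (within-cycle suspension) | Same or reduced dose | Same or reduced dose, unless a repeat suspension | Reduce, if the same toxicity at the same or greater severity forces another suspension in the cycle or at the start of the next |

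**First column.** The table and 9.4.1.1.2 agree that 150 mg Q12H is an allowed restart dose. Section 9.6.5 covers this patient too, because its condition is not limited to persistent or recurrent diarrhoea. It refers only to Section 9.4.1.1.1.1, whose subject is reduction, and to the list of dose levels. Read naturally, it directs a restart at 100 mg Q12H. This is the real disagreement.

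**Second and third columns.** The diarrhoea-specific texts are compatible. The table and 9.4.1.1.4.1 both require a one-level reduction, and an adjusted dose under 9.6.5 is consistent with that.

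**The boundary between columns one and two.** It depends on whether the episode is persistent. Footnote a gives that decision to the investigator without a duration. Section 9.4.1.1.4.1 supplies the only time limit on mandatory reduction of Grade 2 diarrhoea, and it is the same 24 hours that opens the table's suspend-only row. A reader of that section alone could take an episode unresolved at 24 hours on full support to be persistent for that reason, which would leave the suspend-only row little to cover.

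**The case against.** The strongest defence is that the rules form tiers. Row 1 of the table is for Grade 2 diarrhoea unresolved at 24 hours. Row 2 and Section 9.4.1.1.4.1 are for diarrhoea that is persistent or recurrent despite maximal supportive measures. The 24 hours in 9.4.1.1.4.1 is then an added condition on the upper tier, not a trigger of its own, and 9.4.1.1.2 fits this scheme. The defence largely stands. A reader might infer that 9.4.1.1.4.1 flatly contradicts the table for every episode unresolved at 24 hours, but its own qualifiers and footnote a do not support that.

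On 9.6.5, the defence says that adjusting need not mean reducing. Table JPBQ.9.3 includes level 0 (150 mg), and Section 9.4.1.1.1.1 is better read as saying how to reduce than when; otherwise it would override the investigator's discretion over a first Grade 3 hematologic toxicity. This is fair, and it means 9.6.5 does not unambiguously order a reduction. Even so, an instruction to adjust the dose is an odd way to say that it may stay the same.

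Two other inferences fail. One is that the 7-day limit for other nonhematologic Grade 2 toxicity ("Persistent or recurrent Grade 2 that does not resolve with maximal supportive measures within 7 days to baseline or Grade 1") shows 24 hours to be wrong here. Diarrhoea is expressly excepted from that row, and different toxicities may have different limits. The other is that the gap between 150 mg and 100 mg measures the harm. Section 9.4.1.1.2 already permits either dose after a first within-cycle suspension, so sites could differ by legitimate judgment even with perfect wording.

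**Conclusion.** The point holds in a narrow form. For a first Grade 2 episode unresolved at 24 hours, without hospitalization and not judged persistent, Table JPBQ.9.2 and Section 9.4.1.1.2 allow restart at the same dose, while Section 9.6.5 most naturally reads as calling for a lower one. Section 9.4.1.1.4.1 adds uncertainty rather than a second contradiction: it leaves out the suspend-only tier and reuses its 24 hours.

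The consequence is operational: inconsistent restart doses, inconsistent classification of deviations, and possible loss of one of two reduction steps. The documents give no basis for counting the patients affected or estimating lost dose. A reader might infer that the trial's efficacy inference is damaged; nothing here touches alpha, power or event counts.

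The verdict assumes that footnote a's definitions of persistent and recurrent apply to the diarrhoea rows. Its content is general, and part of it concerns hematologic toxicity, so it is not confined to the ALT rows. The verdict also assumes that the table's suspend-only row states the sponsor's intention, which 9.4.1.1.2 supports.

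**What to change.** Two wording changes.

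1. In Section 9.6.5, replace the bullet on recommencing study drug with an instruction to resume dosing per Table JPBQ.9.2.
2. In Section 9.4.1.1.4.1, add that a first Grade 2 episode unresolved at 24 hours, neither persistent nor recurrent, requires suspension only, with resumption at the same dose allowed. State there that the mandatory one-level reduction applies to Grade 2 diarrhoea that is persistent (in the investigator's judgment) or recurrent (within 8 weeks) despite maximal supportive measures, to any diarrhoea requiring hospitalization, and to Grade 3 or 4.

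Whether to keep a time limit for calling diarrhoea persistent is a clinical decision for the sponsor. Removing the limit leaves the matter wholly to investigator judgment; keeping 24 hours requires saying how such an episode differs from the suspend-only tier. If the sponsor in fact wants a reduction at 24 hours in every case, the table's first diarrhoea row is the text to change.

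The cost is a clarification letter or a few lines in an amendment. No procedures are added and the statistical analysis is unchanged.
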